8	CORRELATIVE/ SPECIAL STUDIES	44
8.1	Laboratory Correlative Studies	45
8.1.1	Collection of Specimen(s).....	45
8.1.2	Handling of Specimens(s).....	45
8.1.3	Shipping of Specimen(s)	46
8.1.4	Site(s) Performing Correlative Study	46
8.1.5	Coding of specimens for privacy protection.....	46
9	STUDY CALENDAR.....	47
10	MEASUREMENTS.....	49
10.1	Primary and Secondary Outcome measures.....	50
10.1.1	Measurement Definition	50
10.1.2	Measurement Methods.....	50
10.1.3	Measurement Time Points	50
10.2	Secondary Outcome	50
10.2.1	Tumor necrosis.....	50
10.2.2	Measurement Definition	50
10.2.3	Measurement Methods.....	50
10.2.4	Measurement Time Points	51
10.2.5	Response Review	51
10.3	Secondary Outcome – Proliferation index.....	51
10.3.1	Measurement Definition	51
10.3.2	Measurement Methods.....	51
10.3.3	Measurement Time Points	51
10.3.4	Response Review	51
10.4	Secondary Outcome – Phosphorylation of MEK/ERK.....	51
10.4.1	Measurement Definition	52
10.4.2	Measurement Methods.....	52
10.4.3	Measurement Time Points	52
10.4.4	Response Review	52
11	REGULATORY CONSIDERATIONS.....	52
11.1	Institutional Review of Protocol	52
11.2	Data and Safety Monitoring Plan:	52
11.3	Data Management Plan.....	53
11.3.1	Data Collection	53
11.3.2	Data Submission responsibility	53
11.3.3	Multicenter Guidelines	53
12	STATISTICAL CONSIDERATIONS	53
12.1	Statistical Design and primary analysis	53
12.2	Secondary Analysis	54
12.3	Sample Size	54
12.4	Accrual estimates	54
12.5	Feasibility and safety assessment.....	54
13	REFERENCES.....	55
	Appendix A: Medication guide for patients	58
	Appendix B: Stanford Cancer Institute Serious Adverse Event Reporting.....	58
	Appendix C: ECOG Performance Status	59
	Appendix D: Cockcroft-Gault Formula.....	60
	Appendix E: Ophthalmic exam source sheet	60

PROTOCOL SYNOPSIS

[figure not shown]
In the table below summarize the basic aspects of this research. This is to be used as a quick reference guide.

TITLE	A pilot study of Dabrafenib and Trametinib for patients with BRAF-mutated ameloblastoma
STUDY PHASE	Pilot
INDICATION	Ameloblastoma
INVESTIGATIONAL PRODUCT OR PROCEDURE	Dabrafenib and trametinib
PRIMARY OBJECTIVE(S)	Tumor response rate
SECONDARY OBJECTIVE(S)	Feasibility, safety, pathological response, evidence of molecular pathway inhibition
TREATMENT SUMMARY	Dabrafenib 150 mg po q 12 hours plus trametinib 2 mg once daily.
SAMPLE SIZE	17 evaluable patients
STATISTICAL CONSIDERATIONS	Simon Optimal 2 stage design

IRB application number: IRB-32275

By determination of the Principal Investigator and the IRB, this study is considered IND-Exempt.

SCHEMA

LIST OF ABBREVIATIONS AND DEFINITION OF TERMS

ADL	Activities of daily living
AE	Adverse event
BID	Twice daily
BSA	Body surface area
CBC	Complete blood count
CI	Confidence interval
CRF	Case report/Record form
CR	Complete response
CTCAE	Common Terminology Criteria for Adverse Events
DLT	Dose-limiting toxicity
DSMB	Data Safety Monitoring Board
ECG	Electrocardiogram
GI	Gastrointestinal
Hgb	Hemoglobin
HTN	Hypertension
IRB	Institutional Review Board
IV	Intravenous
LLN	Lower limit of normal
OS	Overall survival
PLT	Platelet
PD	Progressive diseased
PFS	Progression free survival
PR	Partial response
QD	Once daily
RECIST	Response evaluation criteria in solid tumors
RR	Response rate
SAE	Serious adverse event
SD	Stable disease
TTP	Time to progression
ULN	Upper limit of normal
UNK	Unknown
WBC	White blood cell

1.0 OBJECTIVES

1.1 Primary Objectives

To observe the response rate of ameloblastoma to dabrafenib plus trametinib at 6 weeks.

1.2 Secondary Objectives

Secondary endpoints will include feasibility and safety in this patient population. Additionally, response will be assessed pathologically. Two main histologic assays for treatment response will be used: tumor necrosis and phosphorylated-MEK; phosphorylated-ERK; and Ki-67 levels as measured by immunohistochemistry.

2.0 BACKGROUND

2.1 Study Disease

Ameloblastoma is a rare, benign, slow-growing but locally-invasive neoplasm of odontogenic origin involving the mandible (80%) and maxilla with a high recurrence rate attributed to conservative treatment. The neoplasm was first described by Cusack in 1827. {Cusack, 1827} Etymologically, the name derives from the old French word "amel" which means enamel and the Greek word "blastos" meaning germ or bud. Over time, this tumor has been referred to by many different names including "cystosarcoma," "adamantine epithelioma," "adamantinoma," and finally "ameloblastoma." {Ivy, 1930; Malassez, 1885; Wedl, 1870; Brazis, 1995}

Ameloblastoma shows variable geographic prevalence, being the most common benign odontogenic tumor in China {Lu, 1998; Wu, 1985} and Africa {Anand, 1967; Mosadomi, 1975; Barnes, 2005}, while it is the second most common in the United States and Canada {Daley, 1994; Regezi, 1978} (odontoma being most common). Racial bias has also been observed, with African Americans at an overall five-fold increased risk of disease versus Caucasians. {Regezi, 1978} Global incidence has been estimated at 0.5 cases per million person years, with most cases diagnosed in the age range of 30 to 60 years. {Larsson, 1978}

Up to 80% of ameloblastoma cases occur in the mandible, with a particular predilection for the posterior mandibular region. {Reichart, 1995} Rare cases have been reported as primary to the sinonasal cavities. {Schafer, 1998} Often ameloblastoma can be associated with unerupted third molar teeth {Stanley, 1965; Gerzenshtein, 2006; Becelli, 2002} particularly in the unicystic type. Desmoplastic ameloblastomas often occur in the anterior or premolar regions of the mandible or maxilla. Ameloblastic carcinomas also favor the mandible (~2/3) over the maxilla. {Slootweg, 1984} Maxillary ameloblastomas also mostly occur in the posterior molar region.

Histopathologically, ameloblastoma resembles normal odontogenic/enamel epithelium and ectomesenchyme. Odontogenesis consists of chronographic and reciprocal interactions between the ectomesenchymal cells, which are derived from the neural crest, and the oral cavity lining epithelium. {Chai, 2000} The exact origin of ameloblastic epithelium has been hypothesized to arise from: (1) cells from the rests of enamel organ, (2) cells of the sheet of Hertwig's or epithelial cell rest of Malassez, (3) epithelial boundary of an odontogenic cyst, particularly a dentigerous cyst, (4) basal cells of the oral mucosa, and (5)

heterotrophic epithelial from other parts of the body, perhaps pituitary. {Ritchie, 1990; Bhasker, 1981}

Until recently, little was known about the molecular aberrations driving ameloblastoma, due to the tumor's rarity and the fact that technologies to query the tumor genome do not work as efficiently in formalin-fixed paraffin-embedded tissue. However, in 2014, three separate reports, including one from our group at Stanford, profiling ameloblastoma via DNA sequencing were published, all showing the vast majority of tumors to contain somatic mutations impacting the mitogen-activated protein kinase (MAPK) signaling pathway (FGFR2-> RAS -> BRAF) that controls cell proliferation. {Kurppa, 2014; Sweeney, 2014; Brown, 2014}

In particular, all three studies reported a high frequency of BRAF-V600E (valine to glutamic acid substitution at amino acid 600) activating mutations at high allele frequencies in ameloblastomas. In each of these reports, the BRAF-mutated neoplasms were almost exclusively located in the mandible. Two of the three reports went on to characterize the sensitivity of BRAF-mutated ameloblastoma cells to vemurafenib, a V600E targeted small molecule inhibitor FDA-approved for metastatic melanoma. Both studies showed that AM-1, a mandibular-derived ameloblastoma cell line harboring the BRAF-V600E mutation, was exquisitely sensitive to vemurafenib at concentrations similar to BRAF-V600E mutated melanoma and colorectal cancer cell lines.

Surgery is the standard treatment for ameloblastomas. Historically, the extent of resection has been controversial, comprising of two surgical options: "conservative" vs. "radical". The former involves enucleation/curettage of the bony cavity, while the latter involves a radical operation with proper margins. Advantages of enucleation include the fact that it is an outpatient procedure able to be performed by many different service providers (Oral Surgeons and ENT), since it requires no reconstruction. Despite these facts, historical data on simple enucleation demonstrate recurrence rates 60 to 90% and this treatment modality is currently believed to play no role in the management of multicystic ameloblastomas.

The "radical" surgical option is the current standard of care for ameloblastoma, which includes en bloc resection with 1 to 2cm bone margins {Sham, 2009; Carlson, 2006; Gardner, 1980; Williams, 1993; Gortzak, 2006; Becelli, 2011; Pandya, 1972} and immediate bone reconstruction to help with speech and swallowing. {Sham, 2009; Vayvada, 2006; Tsai, 2006; Urken, 1991; Urken, 1998}

The bony margin is defined as the distance away from the radiographic margin predicted to be disease free and oncologically safe to perform osteotomies. Data from 82 ameloblastoma specimens showed microscopic tumor extension 2 to 8mm (mean of 4.5mm) beyond the radiographic boundaries of the tumor. {Carlson, 2006} Hence, the recommended bone margins are 1 to 1.5cm for unicystic and 1.5 to 2cm for solid/multicystic histological types providing increased cure rates. {Wenig, 2007; Becelli, 2002; Carlson, 2006; Zwahlen, 2002; Ueno, 1989; Vayvada, 2006} Ameloblastic carcinoma requires 2 to 3cm bone margins with an elective neck dissection. {Ndukwe, 2010} Therefore surgery for ameloblastoma, when possible, tends to be radical and disfiguring.

Systemic chemotherapy has been attempted a number of times, with numerous agents and combinations being employed (see Table 1) {Gall, 1975; Eliasson, 1989; Ramadas, 1990;

Grunwald, 2001; Campbell, 2003; Amzerin, 2011; Van Dam, 2010}. Anecdotal reports have suggested that ameloblastoma may be sensitive to platinum based agents {Amzerin, 2011} although occasional reports highlight lengthy survival without chemotherapy. {Ciment, 2002; Hasim, 2007} Chemotherapy may also have a role in improvement of clinical symptoms in non-surgical patients. {Ciment, 2002} Much like radiotherapy though, only with continuous reporting of empirical case-based data will the role of systemic chemotherapy be evaluable in this rare entity.

Table 1: Anecdotal reports of Chemotherapy in Ameloblastoma

Case	Regimen	Response	Reference
1	Cyclophosphamide, Methotrexate, 5-Fluorouracil	None	Gall, et al , 1975
2	Vinblastine, Cisplatin, Bleomycin	PR	Eliasson, et al , 1989
3	Adriamycin, Cisplatin, Cyclophosphamide	PR	Ramadas, et al , 1990
4	1st line: 5-Fluorouracil and Cisplatin; 2nd line: Paclitaxel-Carboplatin	PR	Grünwald, et al , 2001
5	Cyclophosphamide	None	Campbell, et al , 2003
6	Doxorubicin and Cisplatin	PR	Amzerin, et al , 2011
7	Gemcitabine and Carboplatin	PR	Van Dam, et al , 2010

2.2 Study Agents

Dabrafenib is a kinase inhibitor indicated for the treatment of patients with unresectable or metastatic melanoma with BRAF-V600E mutation as detected by an FDA-approved test. Dabrafenib is an inhibitor of some mutated forms of BRAF kinases with in vitro IC50 values of 0.65, 0.5, and 1.84 nM for BRAF-V600E, BRAF-V600K, and BRAF-V600D enzymes, respectively. It is manufactured in 50 and 75 mg capsules.

According to the FDA approved package insert, the safety of dabrafenib has been evaluated in 586 patients with BRAF-mutant melanoma, including 181 patients treated for at least 6 months and 86 additional patients for 12 months. The most commonly occurring adverse reactions in these patients treated with dabrafenib were, in order of decreasing frequency hyperkeratosis, headache, pyrexia, arthralgia, papilloma, alopecia, and palmar-plantar erythrodysesthesia syndrome (PPES). The most frequent adverse reactions leading to dose reduction of dabrafenib were pyrexia (9%); PPES (3%); chills (3%); fatigue (2%); and headache (2%).

Dabrafenib has been demonstrated to induce response rates of 52% with a duration median of 5.6 months, in patients with BRAF-mutant melanoma. There are presently no safety or efficacy data for dabrafenib in patients with BRAF-mutant ameloblastoma. Dabrafenib is not FDA approved for treatment of patients with ameloblastoma, therefore conduct of this study will be under either an IND or FDA authorized IND exemption.

Trametinib is a kinase inhibitor of MEK1 and MEK2 FDA-approved for use in patients with metastatic V600E mutated melanoma based upon a randomized control trial (RCT) of trametinib vs chemotherapy in which PFS (4.8 vs 1.5 mo) and RR (22% vs 8%) were

2.3 Rationale

Present accepted standard of care treatment for patients with ameloblastoma is limited to surgical resection and reconstruction. These operations for patients with advanced disease are morbid and disfiguring. There is no defined role for radiation or chemotherapy treatment for ameloblastoma patients at any stage.

Based on the recent discovery of potentially relevant BRAF mutations in ameloblastoma and preclinical data which suggest that BRAF-mutant ameloblastoma may respond to relevant mutant BRAF tyrosine kinase inhibition, we propose to ask in a pilot trial whether there is any evidence of anti-tumor activity against ameloblastoma in patients with advanced disease. Because of robust data with combined BRAF and MEK inhibition in BRAF-mutant melanoma, we plan to use dabrafenib and trametinib in combination. Novartis has agreed to supply both agents for this investigator-initiated study. Because most patients with advanced disease have significant mandibular bone involvement but do not have metastatic disease, we are proposing a trial which will focus on this group of patients. This allows us to ask in a preliminary way whether there is clinical, pathological, or microbiological evidence of anti-cancer activity of a relevant TKI, dabrafenib in combination with a MEK inhibitor, trametinib, in this situation. The design of the trial will facilitate collection of tissue at baseline and after 6 weeks of treatment to allow for assessment of the pathological and microbiological endpoints, but will also not unduly delay attempts at definitive surgical treatment for appropriate patients.

2.4 Study Design

This will be a single-group, single-arm, 2-stage, open non-randomized treatment study whose primary endpoint is tumor response rate with feasibility, safety, pathological and molecular biological secondary endpoints.

2.5 Correlative Studies Background

Activation of the Ras/Raf/MAPK signaling pathway begins with the binding of ligands to receptor-linked tyrosine kinases, such as epidermal growth factor receptor or fibroblast growth factor receptor. This leads to phosphorylation of tyrosine residues on the receptor that then recruits adaptor proteins (eg, GRB2 and SOS). This protein complex allows SOS to switch to an activated state that in turn leads to activation of Ras proteins by binding GTP. This turns on the activity of Raf serine/threonine kinases, including B-Raf (BRAF). The signaling transduction cascade then continues with the phosphorylation and activation of MEK1 and MEK2 tyrosine/threonine kinases. Through phosphorylation, the MEKs activate the Erk MAPKs which regulate transcriptional factors that influence differentiation, senescence, survival, and proliferation.

Mutations in the Ras/Raf/MAPK pathway are essential in a number of cancers including the majority of melanomas with ~50% exhibiting BRAF mutations and ~20% exhibiting NRAS mutations. In melanoma, these mutations appear at an early stage in tumorigenesis, including precursor lesions like benign nevi, and are preserved through progression. These are activating mutations which result in the Ras/Raf/MAPK pathway constitutively signaling for proliferation and survival. Inhibition of this pathway in tumors with BRAF mutations turns off this pathway and shuts down essential survival pathways resulting in cell death. BRAF inhibitor (dabrafenib; formerly GSK2118436) showed promising results with an approximately 2-fold increase in progression-free survival in a phase III trial, which is in a similar range as that of vemurafenib. {Hauschild, 2012}

Recent studies on ameloblastoma have found BRAF-V600E mutations to be present in the majority of cases arising in the mandible. Two studies have demonstrated that cell lines of ameloblastoma are responsive to V600E targeted small molecule inhibitors in cell proliferation assays.

Two main histologic assays for treatment response will be used: tumor necrosis and phosphorylated-MEK, phosphorylated-ERK, and Ki-67 levels as measured by immunohistochemistry. As mentioned above, since the activation of the Ras/Raf/MAPK pathway promotes cell proliferation and survival, blockade of this pathway will result in cell decrease in proliferation, death and necrosis. Furthermore, activation of the Ras/Raf/MAPK pathway leads to phosphorylation of several of the pathway components, including MEK and ERK. These assays for treatment response thus examine both early and late effects of Ras/Raf/MAPK pathway inhibition.

Routine Hemotoxylin-Eosin stained slides from both the pre-treatment biopsy as well as definitive resection specimens will be scored for the presence of tumor necrosis, which will be quantified. Additionally, unstained slides from both pre- and post- specimens from participating institutions will be sent to Stanford University for analysis of phospho-MEK/ERK and Ki-67 staining. Tumors will be scored, by at least two pathologists using percentage positive cells as the primary metric. The results of the

immunohistochemical analysis will be expressed as both raw data in addition to a ratio between pre- and post- treatment

We will also be consenting patients for permission to sequence the genome of their tumor, to publish in public databases anonymized sequence data and to attempt to establish cell cultures of tumor specimens if there is sufficient material to do so. These studies are exploratory and will only be done should there be sufficient specimen from the planned biopsies remaining after the tumor material for tumor necrosis and phosphorylation assays has been obtained.

3.0 PARTICIPANT SELECTION AND ENROLLMENT PROCEDURES

In order to reduce redundancy, we have incorporated the actual eligibility checklist into the body of the protocol.

3.1 Participant Eligibility Checklist

A Participant Eligibility Checklist must be completed in its entirety for each subject prior to registration. The completed, signed, and dated checklist must be retained in the patient's study file and the study's Regulatory Binder.

The study coordinator, treating physician and an independent reviewer must verify that the participant's eligibility is accurate, complete, and legible in source records. A description of the eligibility verification process should be included in the EPIC or other Electronic Medical Record progress note or a signed version of the eligibility checklist must be available in EPIC or other Electronic Medical Record for review.

Eligibility criteria in checklist form

I: Trial information

Protocol Title:	A pilot study of dabrafenib and trametinib for patients with BRAF-mutated ameloblastoma.
Protocol Number:	IRB-32275 / ENT0043
Principal Investigator:	[name]

II. Subject Information:

Subject Name/ID:
Gender:  Male  Female

III. Study Information:

SRC Approved IRB Approved Contract signed

IV. Inclusion/Exclusion Criteria

Inclusion Criteria	Yes	No	Supporting documents
1. Histological diagnosis of ameloblastoma. All stages are eligible. Patients must have evaluable disease by RECIST criteria			
2. BRAF-V600E or other known dabrafenib sensitive BRAF mutation in tumor by any CLIA-certified lab. May include, for example, Sanger sequencing, SNaPshot platform, immunohistochemistry, Foundation One tests, etc)			
3. At least 18 years old			
4. Life expectancy > 3 months			
5. ECOG performance status ≤ 2 (see Appendix C)			


6. Lab values:
 
 • ANC > 1.5 x 10⁹/L • PLT > 99 x 10⁹/L • Hemoglobin > 8 g/dL • Tbili < 1.6 x ULN 
 ○ Except subjects with known Gilbert's syndrome • AST, ALT and alk phos < 2.6 x upper limit of normal (ULN) • Serum creatinine ≤ 1.5 mg/dL, or if serum creatinine is > 1.5 mg/dL, creatinine clearance must be ≥ 50 mL/min (calculate creatinine clearance using the Cockcroft-Gault formula (see Appendix D). • PR / INR and PTT ≤ 1.3 X ULN. Subjects receiving anticoagulation treatment may be allowed to participate with INR established within the therapeutic range prior to randomization 			

7. Ability to understand and the willingness to sign a written informed consent document
			

8. Patients of childbearing potential must agree to use effective contraception until at least 6 months after treatment with dabrafenib and trametinib. See exclusion criteria re pregnancy testing
			

9. Able to swallow and retain oral medication and must not have any clinically significant gastrointestinal abnormalities that may alter absorption such as malabsorption syndrome or major resection of the stomach or bowels
			

10. Left ventricular ejection fraction equal to or greater than normal within 1 month of enrollment. ECHO scans must be used throughout the study.
			

Exclusion Criteria
			

1. No prior treatment with agents targeting BRAF-mutant tyrosine kinases or MEK inhibitors or radiation of target lesions
			

2. Invasive malignancy other than ameloblastoma within 3 years, excluding curatively treated basal cell carcinoma, and other highly curable cancers such as early stage cutaneous squamous cell carcinoma (T1 NO) cervical CIS, early stage prostate cancer, thyroid cancer, breast cancer or history of malignancy with confirmed activating RAS mutation at any time			
3. Uncontrolled hypertension (systolic blood pressure > 140 mm Hg and diastolic blood pressure of > 90 mm Hg which cannot be controlled by anti-hypertensive therapy), CHF, or other major medical illness.			
4. Prior allergic reactions attributed to compounds of similar chemical or biologic composition to dabrafenib or trametinib.			
5. Concomitant use of strong inhibitors (eg, ketoconazole, nefazodone, clarithromycin, gemfibrozil) or strong inducers (eg, rifampin, phenytoin, carbamazepine, phenobarbital, St John's wort) of CYP3A4 or CYP2C8 . For a full list of excluded drugs see Section 4.1.2 of the protocol			
6. Concomitant use of proton pump inhibitors, H2-receptor antagonists, antacids			
7. Known G6PD deficiency			
8. Pregnant or nursing patients. Women of childbearing potential must have a negative SERUM pregnancy test within 14 days of enrollment. Women of child-bearing potential must agree to use effective contraception for 14 days prior to enrollment, throughout the treatment period and for 4 to 6 months after the last dose of study treatment.			
9. EKG with QTcB (Bazett's formula) > 480 ms done within 14 days of enrollment			
10. Interstitial lung disease or pneumonitis.			
11. A history of retinal vein occlusion (RVO).			

12. Congestive heart failure NYHA Class III or worse (Marked limitation of physical activity. Comfortable at rest. Less than ordinary activity causes fatigue, palpitation, or dyspnea.)
			

13. A history of acute coronary syndromes (including myocardial infarction or unstable angina), coronary angioplasty, or stenting within 6 months or a history or evidence of current clinically significant uncontrolled arrhythmias or intra-cardiac defibrillators or abnormal cardiac valve morphology (\geq Grade 2) documented by echocardiogram. Subjects with Grade 1 abnormalities (ie, mild regurgitations/stenosis) may be entered. Subjects with moderate valvular thickening are not eligible. Subjects with atrial fibrillation controlled for $>$ 30 days prior to dosing are eligible.
			

14. Prior systemic anti-cancer treatment (chemotherapy, immunotherapy, biologic therapy, vaccine therapy or investigational treatment within 3 weeks preceding first dose of study treatment, or chemotherapy without delayed toxicity within 2 weeks preceding first dose of study treatment.
			

15. Any serious or unstable pre-existing medical conditions, psychiatric disorders or other conditions which could interfere with the subject's safety, obtaining informed consent, or compliance with study procedures.
			

16. A history of Hepatitis B virus (HBV) or Hepatitis C virus (HCV) infection. Subjects with laboratory evidence of cleared HBV and/or HCV will be allowed.
			

V. Statement of Eligibility

By signing this form of this trial I verify that this subject is [**eligible** / **ineligible**] for participation in the study. This study is approved by the Stanford Cancer Institute Scientific Review Committee, the Stanford IRB, and has finalized financial and contractual agreements as required by Stanford School of Medicine’s Research Management Group.

Treating Physician Signature:	Date:
Printed Name:	

Secondary Reviewer Signature:	Date:
Printed Name:	

Study Coordinator Signature:	Date:
Printed Name:	

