6.2.8 Non-Cutaneous Malignancies

In vitro experiments have demonstrated paradoxical activation of MAP-kinase signaling in BRAF wild type cells with RAS mutations when exposed to BRAF inhibitors, which may lead to increased risk of non-cutaneous malignancies in patients treated with dabrafenib. Cases of RAS-driven malignancies have been seen with BRAF inhibitors. Patients should be monitored as clinically appropriate.

New non-cutaneous malignancies should be reported as a SAE. A biopsy of the new malignancy should be taken, where possible, and submitted for further analyses with the results provided to the PI.

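### Exclusion criterion 1 is worded as a requirement, so it literally says the opposite of its evident intent, and the RAS clause in exclusion criterion 2 is ambiguous

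*Combined protocol and SAP*

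**What the plan says.** Section 3.0 states that the checklist is itself the protocol's eligibility text, and Section 3.1 makes it a precondition for entry: "A Participant Eligibility Checklist must be completed in its entirety for each subject prior to registration". Three people sign it: the treating physician, a secondary reviewer and the study coordinator.

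The first item under the exclusion heading reads: "No prior treatment with agents targeting BRAF-mutant tyrosine kinases or MEK inhibitors or radiation of target lesions".

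The second item opens with "Invasive malignancy other than ameloblastoma within 3 years, excluding curatively treated basal cell carcinoma, and other highly curable cancers such as" and, after naming further cancers, ends with "early stage prostate cancer, thyroid cancer, breast cancer or history of malignancy with confirmed activating RAS mutation at any time".

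On RAS, Section 6.2.8 (Non-Cutaneous Malignancies) describes paradoxical pathway activation in RAS-mutant, BRAF wild-type cells and reports: "Cases of RAS-driven malignancies have been seen with BRAF inhibitors".

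**The concern.** An item under an exclusion heading should describe the patient who may not enter. Item 1 describes the patient who may. A coordinator who follows the words and one who follows the intent would tick opposite boxes for the same patient, and the signed form would not show which reading was used.

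Item 2 raises a different question. Its main rule, no other invasive malignancy within 3 years, is worded correctly. The doubt concerns only the final clause, because nothing marks where the permitted cancers end and a new exclusion begins.

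The protocol gives no rationale for item 1. I infer that it keeps out patients whose response could be altered by earlier BRAF or MEK inhibition, and lesions whose change in size could reflect earlier radiation. Both bear on a response-rate endpoint. The RAS clause bears on patient safety, through the risk that the protocol itself describes.

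**Working it through.** No figure is in dispute on eligibility, so the main check is textual.

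**Item 1: polarity.** For a patient with no BRAF inhibitor, no MEK inhibitor and no radiation to a target lesion, the item's statement is true. A true statement under an exclusion heading means that the patient is excluded. For a patient who has had any of these, the statement is false and the exclusion does not apply. Both outcomes are the reverse of what the trial evidently wants.

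**Item 1: is this a convention of the form?** Item 4 reads "Prior allergic reactions attributed to compounds of similar chemical or biologic composition to dabrafenib or trametinib", which names the excluding condition directly. Items 7, 10 and 11 do the same. The form is not uniform: item 8 adds requirements on pregnancy testing and contraception, and items 13 and 16 add sentences on who may enter. But item 8 opens with the excluding condition, whereas item 1 consists only of the negated one.

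**Item 1: is it stated correctly elsewhere?** The synopsis, Section 2.4 and Section 4.0 do not restate it. Exclusion 14 covers prior systemic anti-cancer treatment only within 3 weeks of the first dose (2 weeks for chemotherapy without delayed toxicity). It does not catch a BRAF or MEK inhibitor given earlier, and no other exclusion mentions prior radiation of target lesions. Such patients are conceivable: Section 2.2 describes one ameloblastoma patient treated off-label with dabrafenib and cites a published response to BRAF-targeted treatment.

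**Item 2: two readings of the RAS clause.**

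| Reading | For | Against |
|---|---|---|
| Last member of the permitted list | Joined by a conjunction to the preceding cancer; no semicolon, line break or number closes the list | The list is of highly curable cancers, and a history of RAS-mutant malignancy is not one |
| Separate exclusion | Its open-ended time frame contrasts with the 3-year limit of the main rule; Section 6.2.8 gives a safety reason | Nothing in the punctuation or layout separates it |

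The second reading is the likelier intent; the text alone does not settle it. No other eligibility item mentions RAS, so a RAS-mutant malignancy more than 3 years old is addressed only here.

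**Design figures (Section 12.1).** Inputs: 9 then 8 patients, stop at 0/9, reject at 3 or more of 17. With X1 ~ Bin(9, p) and X2 ~ Bin(8, p),

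P(reject) = P(X1=1)·P(X2≥2) + P(X1=2)·P(X2≥1) + P(X1≥3).

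- p = 0.05: 0.2985×0.0572 + 0.0629×0.3366 + 0.0084 = 0.0466 (stated 0.0466).
- p = 0.25: 0.2253×0.6329 + 0.3003×0.8999 + 0.3993 = 0.8122 (stated 0.8122).
- Early stopping at p = 0.05: 0.95^9 = 0.630 (stated 0.63).

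All three reproduce. They depend only on the sample sizes, the cut-offs and the assumed response rates, so rewording the criteria changes none of them.

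**The case against.** The strongest reply is that nobody would apply item 1 literally. Doing so would bar nearly everyone the trial is for, so the error exposes itself. Section 3.1 has the coordinator, treating physician and an independent reviewer verify eligibility, and Section 11.3.1 requires the PI or a designee to confirm it centrally before enrolment. The form gives no instruction that a Yes decides the matter; signatories declare the patient eligible or ineligible separately.

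Most of this stands, and it limits the practical risk. It does not remove the defect. Those checking have no correctly worded rule to check against, and Section 11.1 bars any site from modifying the protocol on its own. The missing scoring instruction adds to the uncertainty about what a tick means.

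On item 2, the objection is that the clause reads naturally as a second exclusion. A reader might infer the opposite: that the criterion is reversed and plainly admits RAS-mutant malignancy. The documents do not support that stronger reading. The main clause is correct, the differing time frames point to a separate exclusion, and Section 6.2.8 points the same way. What stands is ambiguity.

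**Conclusion.** The point holds for both items, to different degrees. Item 1 is a clear wording error in the operative eligibility text: its literal meaning is opposite to its evident intent, and it is not corrected elsewhere. Item 2 is ambiguous in its RAS clause only.

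The expected consequence is inconsistent or wrong checklist entries, and perhaps an occasional misclassified patient. The documents give no basis for estimating how often. A reader might infer that the trial would in practice enrol only pre-treated patients, or that its error rates are compromised. Neither follows: the intent is recoverable, central confirmation is in place, and the Section 12.1 figures do not depend on this wording.

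The conclusion assumes that item 1 was meant to exclude pre-treated patients and irradiated target lesions, and that the RAS clause was meant to exclude. The second assumption is less certain than the first, and the sponsor should confirm both.

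**What to change.** 1. The sponsor confirms the intended meaning of both items.
2. If confirmed, item 1 is rewritten as an excluding condition: prior therapy with an agent targeting mutant BRAF or with a MEK inhibitor, or prior radiotherapy to a target lesion.
3. The RAS clause is taken out of the exception list in item 2 and set as a sentence or numbered item of its own, with its effect on eligibility stated and reconciled with Section 6.2.8.

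The cost is two lines of checklist wording in the next amendment, issued to all sites as a single version under Section 11.1. No procedure, patient or statistical calculation changes.
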